4.5.2.1. Adverse Events of Special Interest

No adverse events of special interest (AESI) are identified for the study therefore no statistical analysis will be performed for AESI.

4.5.3. Additional Safety Assessments (if applicable)

4.5.3.1. Laboratory Data

Laboratory evaluations including the analyses of chemistry laboratory tests, hematology laboratory tests and urinalysis will be based on GSK Core Data Standards.

Table 2 Parameters of laboratory tests assessments

Laboratory Tests	Parameters	
Hematology	• Platelet count	
	• Red blood cell (RBC) count	
	RBC indices	
 • Mean corpuscular volume (MCV) • Mean corpuscular hemoglobin (MCH) • %Reticulocytes
	Absolute WBC count with differential:	
 • Neutrophils • Lymphocytes • Monocytes • Eosinophils • Basophils
	• Hemoglobin	
	• Hematocrit	
Clinical chemistry¹	
 • Urea • Potassium • Creatinine* • Sodium • Calcium • Glucose fasting • Creatine phosphokinase (CPK) 	
 • Aspartate aminotransferase (AST)/serum glutamic-oxaloacetic transaminase (SGOT)¹ • Alanine aminotransferase (ALT)/serum glutamic-pyruvic transaminase (SGPT)¹ • Alkaline phosphatase² • Total bilirubin¹ • Direct bilirubin, only if total bilirubin is elevated • Total protein
Routine urinalysis	
 • Specific gravity • pH, glucose, protein, blood, ketones, [bilirubin, urobilinogen, nitrite, leukocyte esterase] by dipstick • Microscopic examination. Please note, this will only be performed if there is an abnormality in accordance with Clinical Laboratory standard procedures at investigator discretion. • Culture at investigator discretion (if positive: specify pathogen) 	

Laboratory Tests	Parameters
Hematology	
 • Platelet count
	
 • Red blood cell (RBC) count
Other screening tests	
 • FSH and estradiol (as needed in WONCBP only) • Cotinine, alcohol and drug screen (to include at minimum: amphetamines [including XTC], methadone, barbiturates, cocaine, opiates, cannabinoids and benzodiazepines) • Serology [(HIV antibody 1/2 antibody test, hepatitis B surface antigen [HBsAg], and hepatitis C virus antibody)] • Testing for SARS-CoV-2 may be performed at the discretion of the physician and based on local guidelines.

NOTES

1. Details of liver chemistry stopping criteria and required actions and follow-up are given in Section 10.6 of the protocol. Liver Safety: Suggested Actions and Follow-up Assessments [and Study Intervention Rechallenge Guidelines]. All events of ALT [or AST] $\geq 3 \times$ ULN and total bilirubin $\geq 2 \times$ ULN (>35% direct bilirubin) or ALT [or AST] $\geq 3 \times$ ULN and INR >1.5 (if INR measured), which may indicate severe liver injury (possible Hy's law), must be reported to [sponsor] in 24hours (excluding studies of hepatic impairment or cirrhosis).
 2. If alkaline phosphatase is elevated, consider fractionating.
- * To assess the kidney function, use eGFR 2009 calculator (CKD-Epi creatinine equation). eGFR (based on CKD-Epi) will be measured at all time points when creatinine is measured.

Descriptive statistics (n, mean, standard deviation (SD), median, minimum value (min), and maximum value (max)) will be presented for quantitative measurements of absolute value for continuous laboratory parameters at baseline and each assessed visit on-treatment period. Counts and percentages will be produced for qualitative measurements measure laboratory parameters.

Participants listing of all clinical laboratory data will be produced for each treatment and period in Safety.

If a laboratory value which is expected to have a numeric value for summary purposes, has a non-detectable level reported in the database, where the numeric value is missing, but typically a character value starting with '<=' or '>=' (or indicated as less than x or greater than x in the comment field) is present, the number of significant digits in the observed values will be used to determine how much to add or subtract in order to impute the corresponding numeric value.

- Example 1: 2 significant digits = '<= x' becomes $x - 0.01$
- Example 2: 1 significant digit = '>= x' becomes $x + 0.1$
- Example 3: 0 significant digits = '<=x' becomes $x - 1$

Details of the planned displays for clinical laboratory evaluations are provided in Output programming specifications (OPS) and will be based on GSK Data Standards and statistical principles.

4.5.3.2. Vital Signs

The analyses of vital signs parameters will be based on GSK Core Data Standards (IDSL).

The following vital signs measurements will be measured in a supine position after 5 minutes rest at baseline and each assessed visit.

- Systolic and Diastolic blood pressure
- Pulse rate

Descriptive statistics (n, mean, standard deviation (SD), median, minimum value (min), and maximum value (max)) will be presented at baseline, absolute value of vital signs parameters at each assessed visit for on-treatment period.

Participants listing for all vital signs data will be produced for each treatment and period in Safety.

Details of the planned displays for vital signs parameters are provided in Output programming specifications (OPS) and will be based on GSK Data Standards and statistical principles.

4.5.3.3. ECG

All ECGs will be performed as single assessments at the following times: during screening, upon admission, every morning on dosing days for each TP at pre-dose, 20±10 minutes post-dose, and at follow-up. In case of any QT abnormalities ECGs will be repeated in triplicate. ECG measurements will be recorded, including heart rate (HR), PR interval, QRS duration, QT interval, and QTc interval. QT intervals will be based on Fridericia's formula and reported as per captured in eCRF:

Descriptive statistics (n, mean, standard deviation (SD), median, minimum value (min), and maximum value (max)) will be presented at baseline, and absolute and change from baseline for HR, QTc and other ECG parameters at each assessed visit for overall (on and post treatment) and on-treatment period.

Participants listings will be provided for 12 lead ECGs values and findings including abnormal ECGs for each treatment sequence and period in Safety.

Details of the planned displays for ECG parameters are provided in Output programming specifications (OPS) and will be based on GSK Data Standards and statistical principles.

4.5.3.4. Pulmonary Tests

Spirometry will be performed at the study site to assess FEV1 and FVC.

At least 3 acceptable spirometry maneuvers (from a maximum of 8 attempts) should be achieved on each occasion that spirometry assessments are performed, in accordance with the American Thoracic Society/European Respiratory Society standards [Graham, 2019]. The highest of 3 technically acceptable measurements will be recorded at each visit. Global Lung Function Initiative equations will be used to determine predicted values. Predicted values will be corrected for gender, age, height and race.

Descriptive statistics (n, mean, standard deviation (SD), median, minimum value (min), and maximum value (max)) will be presented at baseline, and absolute and change from baseline for FEV1 and FVC parameters at each assessed visit for overall (on and post treatment) and on-treatment period.

4.5.3.5. LVEF

Not Applicable.

4.6. Other Analyses**4.6.1. Subgroup analyses**

No subgroup analysis will be performed for the study.

4.6.2. Other variables and/or parameters

No other variables/parameters will be defined for the study.

4.6.3. Analyses to Support Regional Submission

No analysis will be performed for regional submission.

4.7. Interim Analyses

No planned interim analyses.

4.8. Changes to Protocol Defined Analyses

There was one change to the originally planned statistical analysis specified in the protocol (Dated: [14 May 2024]).

An additional FAS analysis set has been added to the Analysis set table.

5. SAMPLE SIZE DETERMINATION

Up to 24 healthy participants will be randomly assigned to ensure at least 20 participants are included in the MCC analysis set with 10 randomized to each treatment sequence.

The target number of participants is chosen to achieve half width (refer to [Table 3](#)) of the 90% CI, in the estimate of the GMR for the primary endpoint.

An MCC study [[Del Donno](#), 1988] reported a within-participant coefficient of variation (CV_w) of 8.5% for the AUC_{0-6h} parameter. The within-participant CV_w for the AUC_{0-4h} parameter was thus assumed to range from 8.5 % to 11.5%.

Using a sample size 20 and CV_w of 10.5% in AUC_{0-4h}, the half width of the upper bound of 90% CI for observed treatment ratio of AUC_{0-4h} between two treatment arms is 5.93 % ([Table 4](#)). Considering for example, that the GMR between Test and Reference is 1.05 for n = 20 and CV_w = 10.5%, then the upper bound of the 90% CI for observed treatment ratio is $1.05 \times (1 + 0.0593) = 1.11$ and the lower bound is $1.05 / (1 + 0.0593) = 0.99$ (ii).

Table 3 Half-width Expected for Different Sample Size and Intra-Subjects Variability

Sample size	Intra subject variability SD (CV _w %)	Half-width (%) of the upper bound of 90% CI for Observed Treatment Ratio
16	0.0849 (8.5%)	5.44
18		5.07
20		4.77
22		4.52
16	0.0948 (9.5%)	6.09
18		5.68
20		5.35
22		5.06
16	0.1047 (10.5%)	6.76
18		6.30
20		5.93
22		5.61
16	0.1146 (11.5%)	7.42
18		6.92
20		6.51
22		6.16

Abbreviations: CI=confidence interval; CV_w=coefficient of variation within subject

Table 4 Lower and Upper Bound GMR for Different Values of GMR

GMR (T/R)	Lower and Upper bound for observed GMR (T/R)	
	Lower Bound	Upper Bound
0.9	0.85	0.95
0.95	0.90	1.01
1	0.94	1.06
1.05	0.99	1.11
1.1	1.04	1.17

Note: n = 20 & CVw = 10.5%

Abbreviations: CVw=coefficient of variation within subjects, GMR=geometric mean ratio, R=reference, T=test.

6. SUPPORTING DOCUMENTATION

6.1. Appendix 1 Study Population Analyses

The study population analyses will be based on the FAS and enrolled participants, unless otherwise specified. A summary of the number of participants in each of the participant level analysis set will be provided.

Study population analyses will be included in analyses of participant's disposition, protocol deviations, demographic and baseline characteristics, prior and concomitant medications etc. based on GSK Core Data Standards.

6.1.1. Participant Disposition

Participant disposition will be tabulated by each treatment sequence for all participants combined with the counts and percentages of participants who complete the study, prematurely withdraw, and the reason for study withdrawal for FAS and enrolled participants.

Summary of treatment status and reasons for discontinuation of study treatment will be produced for study treatment, with the number of participants who completed study treatment, or prematurely discontinued treatment, and the primary reasons for treatment discontinuation tabulated for the FAS.

Participant listing of the reasons for study withdrawal will be provided for each treatment sequence and period in enrolled participants.

Summary of screen failure (did not meet inclusion/exclusion criteria, AE, SAE and other) and its reason will be provided for overall (Total) screened participants.

Table will be generated for summarizing the number of participants in each analysis set for all participants who provided informed consent.

6.1.2. Demographic and Baseline Characteristics

Demographic characteristics and baseline characteristics such as age, age group, sex, race, ethnicity, childbearing potential, height, weight, and body mass index (BMI) will be summarized and tabulated by treatment sequence and overall (Total) using participants in FAS and enrolled participants. Listing for demographic characteristics will be produced in FAS for each treatment sequence.

Descriptive statistics will be presented for age, height, weight, and BMI. Counts and percentages will be presented for sex, race, ethnicity.

6.1.3. Protocol Deviations

Important protocol deviations will be summarized for FAS in overall (Total) participants. Listing of important protocol deviation will also be generated for each treatment and period in FAS.

A summary of inclusion and exclusion criteria will be produced for FAS in overall (Total) participants.

Listing for participants with inclusion/exclusion criteria deviations will be generated for each treatment sequence in FAS.

Protocol deviations will be tracked by the study team throughout the conduct of the study. These protocol deviations will be reviewed to identify those considered as important as follows:

- Data will be reviewed prior to freezing the database to ensure all important deviations (where possible without knowing the study treatment details) are captured and categorized in the protocol deviations dataset.
- This dataset will be the basis for the summaries of important protocol deviations.
- Data will be reviewed prior to freezing the database to ensure all deviations leading to analysis population exclusions are captured and categorized in the protocol deviations ADaM dataset (note these exclusions are not captured in the SDTM dataset).

6.1.4. Prior and Concomitant Medications

Prior and Concomitant medications will be coded using WHO Drug dictionary version on or after Global B3 Sept 2023.

Multi-ingredient term concomitant medications will be presented according to their combination ATC classification rather than the classifications of the preferred term.

A concomitant medication will be summarized (number and percentage) by ATC 1 and ingredient for FAS in each period (pre/on/post) in which it was taken, so a concomitant medication that was started in the screening and stopped during active treatment will appear in both the pre-treatment and the on-treatment tables.

Concomitant medications include any medication that was taken at some point during the on-treatment period as defined in Section 6.9 of the protocol.

Participants listing of concomitant medication will also be generated for FAS.

6.1.5. Medical History and Current Medical Conditions

Listings for medical history and current medical conditions will be presented for each body system of participants for FAS.

6.2. Appendix 2 Electronic Clinical Outcome Assessment (eCOA) Compliance

Not applicable

6.3. Appendix 3 Data Derivations Rule

Not applicable

6.3.1. Criteria for Potential Clinical Importance

Not applicable

6.3.2. Study Period

Assessments and events will be classified according to the time of occurrence relative to the study treatment period (days).

Pre-Treatment : For the presentation of serious adverse events (SAEs), concomitant medications, and other assessments in pre-treatment is defined as -

Date of assessment < Study treatment start date of period 1 (Day 1).

On-Treatment : For the presentation of adverse events (AEs), serious adverse events (SAEs), concomitant medications, 12-lead ECG, vital signs, and other assessments in on-treatment is defined as -

Study treatment start date of period 1 (Day 1 of Period 1) <= Date of assessment < Study treatment stop date of period 2 (Day 8 of Period 2) or early withdrawal + 1 days

If time of assessment or study treatment is not collected (missed), the following assessment on the first dose date will be assumed to be taken prior to the first dose and therefore considered pre-treatment .

Post-Treatment : For the presentation of adverse events (AEs), serious adverse events (SAEs), concomitant medications, 12-lead ECG, vital signs and laboratory assessments in post-treatment is defined as

Date of assessment > Study treatment stop date of period 2 (Day 8 of Period 2) or early withdrawal + 1 days.

Please refer Section 6.3.5 for handling of missing and partial dates of assessments.

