4. STUDY DESIGN

4.1. Overall Design

This is a randomized, double-blind, single-site, 2-way crossover study to assess the effect of repeated doses of Test propellant (HFA-152a, aka 1 – Difluoroethane) on MCC as compared to Reference propellant (HFA-134a, aka 1,1,1,2 – Tetrafluoroethane) in healthy male and female participants.

The study has planned to enrol a total of 24 healthy participants to ensure at least 20 participants are included in the principal stratum analysis set with at least 10 participants randomized to each treatment sequence.

Participants will be randomly assigned to 1 of 2 treatment sequences in 2 TPs using a cross-over design. The following treatment sequences will be tested:

- Treatment Sequence 1: T-R
- Treatment Sequence 2: R-T

[figure not shown]
Where T is HFA-152a, aka 1 – Difluoroethane (Test) and R is HFA-134a, aka 1,1,1,2 – Tetrafluoroethane (Reference).

In each study period, Test or Reference propellants will be administered by oral inhalation BID on Days 1-6 and as a single dose on the morning of Day 7. MCC will be determined using gamma-scintigraphy following the administration of nebulized colloidal ^{99m}Tc-sulphur colloid by inhalation after the final dose of the propellant on Day 7. The

study will comprise a Screening Period of up to 21 days prior to first dosing; 2 TPs of 8 days each, with a 7 ± 2 days Washout Period between the 2 TPs; and a final safety Follow-up Visit up to 8 ± 2 days after the final dose administration in TP2 (maximal duration 56 days).

A schema of the study is provided in Figure 1.

Figure 1 Schematic of the Study

Notes: Training MDI concerns the initial training of the inhalation from MDI (propellants); additional training will be provided during the treatment periods. Between Day 1 to Day 6 of Period 1, the ROI encompassing the right lung will be defined based on a single ^{57}Co transmission scan of the participant chest. Green triangles represent propellant administrations (4 inhalations BID for 6 days + single morning administration on Day 7). Tc Training inhalation concerns the training of inhalation of nebulized saline solution (without radiolabeled $^{99\text{m}}\text{Tc}$); Yellow boxes represent inhalation of the nebulized labelled $^{99\text{m}}\text{Tc}$ for the assessment of MCC.

Abbreviations: BID=twice daily, Co=Cobalt, MDI=metered dose inhaler, ROI=region of interest, Tc=Technetium.

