4.5.2. Adverse Events

The applicable definition of an AE and SAE are in the study protocol Sections 8.4 and 10.3. All reported AEs will be coded using the standard GSK dictionary, (MedDRA ≥ 26.1 version).

An AE is considered study treatment emergent (on-treatment) if the AE onset date is on or after study treatment start date and on or before study treatment stop date plus 1 day (inclusive) follow-up or worsens (change in AE severity from lower severity to higher severity category) relative to the pre-study treatment state.

AEs occurring following dosing in a specific period but before dosing in the next period will be attributed to that specific period. If the time is missing for an AE on a dosing day then the AE will be attributed to the treatment given on that day.

Overview of AEs:

The following points will be presented in a summary table for overview of AEs in overall (on and post-treatment) and on-treatment period.

- Total number of AEs reported with the number of participants who experienced at least 1 AE
- AE by maximum severity intensity

- Drug-related AE and SAE, fatal SAE, drug-related fatal SAE, non-fatal SAE, drug-related non-fatal SAE
- AE leading to discontinuation of study treatment and AE leading to withdrawal from study

AEs and SAEs by SOC and PT:

The below summaries (counts and percentages) will be produced for AEs and SAEs by system organ classes (SOC) and (PT) for overall (on- and post-treatment) and on-treatment period.

- Summary of AEs by SOC and PT
- Summary of SAEs by SOC and PT
- Summary of SAEs by SOC and PT with number of subjects and occurrences

Common AEs:

The following summaries (counts and percentages) will be displayed for common ($\geq 10\%$ incidence, before rounding) AEs for overall (on- and post-treatment) and on-treatment period.

- Summary of common ($\geq 10\%$) AEs by PTs
- Summary of common ($\geq 10\%$) Non-SAEs by SOC and PTs with number of subjects and occurrences
- Summary of Non-SAEs (0-5%) by SOC and PTs with number of subjects and occurrences
- Summary of common ($\geq 10\%$) SAEs by SOC and PTs with number of subjects and occurrences

AEs and SAEs related to study treatment:

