6.3.5. Handling of Partial Dates

Element	Reporting Detail		
General	
 Partial dates will be displayed as captured in participant listing displays. However, where necessary, display macros may impute dates as temporary variables for sorting data in listings only. In addition, partial dates may be imputed for 'slotting' data to study phases or for specific analysis purposes as outlined below. Imputed partial dates will not be used to derive study day, time to onset or duration (e.g., time to onset or duration of adverse events), or elapsed time variables (e.g., time since diagnosis). In addition, imputed dates are not used for deriving the last contact date in overall survival analysis dataset. 		
Adverse Events	
 Partial dates for AE recorded in the CRF will be imputed using the following conventions: 
 
 Missing start day	 
If study intervention start date is missing (i.e. participant did not start study intervention), then set start date = 1st of month.
 
Else if study intervention start date is not missing:
 
 If month and year of start date = month and year of study intervention start date, then 	
 
 	Missing start day	
If study intervention start date is missing (i.e. participant did not start study intervention), then set start date = 1st of month.
 
Else if study intervention start date is not missing:
 
 If month and year of start date = month and year of study intervention start date, then
Missing start day	
If study intervention start date is missing (i.e. participant did not start study intervention), then set start date = 1st of month.
 
Else if study intervention start date is not missing:
 
 If month and year of start date = month and year of study intervention start date, then 		

Element	Reporting Detail	
		
 – If stop date contains a full date and stop date is earlier than study intervention start date, then set start date= 1st of month. – Else set start date = study intervention start date. 
Else set start date = 1st of month.

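### SAP 6.3.2 puts the day after treatment stop in neither the on-treatment nor the post-treatment period, labels the stop as Day 8 although dosing ends on Day 7, and treats the washout as on-treatment

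*SAP*

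**What the plan says.** SAP 6.3.2 defines one on-treatment window for the whole study. It opens at "Study treatment start date of period 1 (Day 1 of Period 1) <= Date of assessment" and closes at "Date of assessment < Study treatment stop date of period 2 (Day 8 of Period 2) or early withdrawal + 1 days". Post-treatment is defined by "Date of assessment > Study treatment stop date of period 2 (Day 8 of Period 2) or early withdrawal + 1 days".

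SAP 4.5.2 has its own rule for AEs: an event is on-treatment if it starts "on or before study treatment stop date plus 1 day (inclusive) follow-up". The same section attributes events by period: "AEs occurring following dosing in a specific period but before dosing in the next period will be attributed to that specific period". It presents AEs in a "summary table for overview of AEs in overall (on and post-treatment) and on-treatment period", so overall is the sum of the two classes.

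On dosing, protocol 4.1 gives the propellant twice daily on Days 1 to 6 and then "as a single dose on the morning of Day 7". Protocol 4.3 and SAP 1.2 agree. In the Schedule of Activities, Day 8 is the discharge day. SAP 4.5.1 measures exposure to the date of the last dose.

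For an AE with a missing start day in the month of first dosing, SAP 6.3.5 makes one exception, for a complete stop date before first dose. Otherwise it applies "Else set start date = study intervention start date".

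**The concern.** Three things do not fit together.

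- **Operators.** The two inequalities in 6.3.2 are both strict and use the same date, so they do not meet.
- **Anchor.** The stop date is labelled with a day on which no propellant is given. A programmer must choose between the label and the recorded last dose. The choice decides which date goes unclassified.
- **Two rules.** Sections 4.5.2 and 6.3.2 both define on-treatment for AEs, with different limits and no order of precedence.

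In addition, a window without a break between periods puts the only washout inside on-treatment time, and 4.5.2 credits its AEs to the first propellant. The equivalent drug-free time after Period 2 is post-treatment.

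Safety is a stated secondary objective. The system organ class and preferred term tables of drug-related AEs are planned for the on-treatment period, so these definitions decide what those tables contain. If the ambiguity stays until programming, it may be settled after data have been seen.

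**Working it through.** **Calendar.** Inputs are from protocol 4.1 and 4.3 and SAP 1.2: screening up to 21 days, two periods of 8 days, washout 7 ± 2 days, follow-up 8 ± 2 days.

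- Maximum duration: 21 + 8 + (7 + 2) + 8 + (8 + 2) = 56 days, the stated figure.
- Doses per period: 6 × 2 + 1 = 13, the stated figure, so the last dose is on Day 7. The radiolabelled inhalation is also on Day 7, so counting it as study treatment does not move the stop to Day 8.
- With a washout of w days (5, 7 or 9), Period 2 Day 1 is study day 8 + w + 1 = 14, 16 or 18.

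**Unclassified date.** Let S be the stop date. On-treatment needs date < S + 1 and post-treatment needs date > S + 1. Date = S + 1 meets neither. Three readings of 6.3.2 are possible:

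| Reading | On-treatment ends | Post-treatment starts | In neither (Period 2) | Study day for w = 5 / 7 / 9 |
|---|---|---|---|---|
| S = Day 8, + 1 applied (literal) | Day 8 | Day 10 | Day 9 | 22 / 24 / 26 |
| S = Day 8, + 1 for early withdrawal only | Day 7 | Day 9 | Day 8 | 21 / 23 / 25 |
| S = actual last dose Day 7, + 1 applied | Day 7 | Day 9 | Day 8 | 21 / 23 / 25 |

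Exactly one date is lost each time. Day 9 has no scheduled assessment: follow-up falls on Day 14 to 18 counted from discharge (Schedule of Activities) or Day 13 to 17 counted from the last dose (protocol 4.1). Day 8 has vital signs and spirometry, and no spirometry is scheduled at follow-up. For an early withdrawal the lost date is the day after withdrawal.

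**Comparison with SAP 4.5.2 at the end of Period 2.**

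- Both sections use Day 8: 4.5.2 includes Day 9, and 6.3.2 leaves it unclassified.
- Both use Day 7: 4.5.2 includes Day 8, and 6.3.2 leaves it unclassified.
- 4.5.2 uses Day 7 and 6.3.2 uses Day 8: on-treatment ends on Day 8 in both, but Day 9 is still outside post-treatment.

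If 4.5.2 is read period by period, washout time after stop + 1 is not on-treatment, which again disagrees with 6.3.2.

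**Length of the on-treatment window (literal reading).**

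- Period 1: 8 + w = 13, 15 or 17 days. Period 2: 8 days.
- Ratios: 13/8 = 1.6, 15/8 = 1.9, 17/8 = 2.1.
- On-treatment days after the last dose: 1 + w = 6, 8 or 10 in Period 1, against 1 in Period 2.
- If Day -1 of Period 2 is counted outside the washout, Period 1 has 14, 16 or 18 days. The sum that gives 56 has no separate day for it, so 13 to 17 fits the stated maximum.

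In the overall tables Period 2 gains the follow-up and reaches Day 13 to 17 (or 14 to 18), less the unclassified date. That roughly matches Period 1.

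**Partial dates.** Period 2 Day 1 comes 8 + w = 13 to 17 days after Period 1 Day 1. Assuming a 30-day month, both fall in one month when first dosing is no later than the 17th (30 − 13) or the 13th (30 − 17). A Period 2 AE with a missing start day is then set to Period 1 Day 1 and credited to the other propellant.

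**After the fix below.** Each period has Day 1 to Day 8 = 8 on-treatment days, and no date is unclassified.

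**The case against.** The strongest reply is that little is lost on the SAP's own wording. With the stop at Day 8, the unclassified date is Day 9, when nothing is scheduled. The planned listings of AEs, vital signs and laboratory data would still show any record from that day. The safety analysis is descriptive, with no formal comparison. Attributing washout events to the preceding period is an explicit, prespecified choice. Randomization is 1:1 to the two sequences, so the longer first window falls about equally on each propellant, and the overall tables are roughly balanced. Confinement from Day -1 to Day 8 should make missing onset days rare. All of this stands, and it limits the size of the point.

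It does not remove the defect. AEs, concomitant medications and unscheduled data can still fall on Day 9, and an AE that does would be missing from the overall tables if 6.3.2 governs. The stop label still disagrees with the dosing schedule, and the SAP still has two AE rules without precedence.

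A reader might infer that people who leave after Period 1 contribute only the long window and so unbalance the propellants. The documents do not support this: 6.3.2 cuts the window at early withdrawal + 1 day, so someone who withdraws at Period 1 discharge or during the washout has a shortened one. Nor are drug-related AEs tabulated for the on-treatment period alone, because the overview table in 4.5.2 also gives them for the overall period.

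**Conclusion.** The point holds and is minor. SAP 6.3.2 leaves one calendar date per participant unclassified under every reading. That date is Period 2 Day 9 as written, or Day 8 if programmed from the last dose. The Day 8 stop label disagrees with the Day 7 last dose. The conflict with 4.5.2 arises when both sections use the same stop date.

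The on-treatment window is about 13 to 17 days for the first propellant against 8 for the second, on the literal reading. That the washout counts for Period 1 is inferred from 6.3.2 and 4.5.2 together, since 6.3.2 itself names no period for it. The main effect is to inflate on-treatment counts.

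Two stronger conclusions are tempting. One is that scheduled Day 8 vital signs and spirometry will be lost. That follows only if the recorded last dose replaces the stated Day 8, or if the extra day is taken to apply to early withdrawal alone. The other is that the comparison between propellants is materially biased. With 1:1 sequences the documents give no ground for that.

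The primary mucociliary clearance analysis is unaffected.

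**What to change.** Use one definition in SAP 4.5.2 and 6.3.2, set for each period:

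- **On-treatment:** first dose of the period to the actual last dose of that period (planned Day 7) + 1 day, inclusive.
- **Post-treatment:** any later date, up to the first dose of the next period or final discharge.
- Remove the Day 8 label from the stop date.
- Keep the existing attribution of washout AEs to the preceding period for the overall tables.
- For an AE with a missing start day, use the visit or period in which it was reported before defaulting to Period 1 Day 1.

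The cost is SAP wording and derivation code. No data collection changes. The change should be made before unblinding.
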